### 1.2.1 Clinical trials using methylphenidate for treatment of fatigue

Methylphenidate is a central nervous system stimulant similar to amphetamine with a short plasma half-life of 2 hours, a rapid onset of action, and duration of action of 3 to 6 hours (43). The baseline dose is usually 5 mg in the morning and at noon with titration as needed with a maximum dosing of 1 mg/kg/d. The most frequent side effects are tachycardia, nervousness, insomnia, and anorexia, especially at higher doses. Open-label studies suggest an improvement in fatigue (44, 45).

In a randomized controlled trial, 112 patients were assigned to 5 mg of methylphenidate or placebo and able to repeat dosing every 2 hours as needed to a maximum of 20 mg daily. At 7 days, significant improvement in fatigue compared to baseline was noted in both groups (46). The authors suggested that the observed benefits might be due to daily contact with the study nurse which may have had a major symptomatic or placebo effect.

A more recent study conducted by Moraska et al, reports the results of a randomized, controlled trial comparing methylphenidate versus a placebo in a group of heterogeneous group of patients with CRF (47). Adults who were eligible for this trial had to have a history of CRF as defined by a score of 4 or more on a subjective fatigue level screening scale that ranged from zero (none) to 10 (as bad as it can be), for at least 1 month before registration. The authors found no significant differences in usual fatigue, current fatigue or worse fatigue during the course of the 4 week study. The primary end point of prorated Area Under the Curve for the usual fatigue question of the BFI did not show a statistically significant difference between the methylphenidate and placebo arms ( $P=.32$ ). The methylphenidate treatment arm demonstrated a 3.2% better fatigue score on average, which was 16% the standard deviation of the fatigue scores (a small effect size) and not significantly different than that in the placebo arm. The authors did observe however, that patients with more advanced disease showed a significant response to methylphenidate as well as a trend for more improvement in usual fatigue for those who reported more severe fatigue at baseline with methylphenidate as opposed to placebo. This study excluded

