#### 4.0 TEST SCHEDULE

Test Schedule Table

	Active-Monitoring Phase			
	≤28 days prior to registration	Baseline	End of Week 4 (Cycle 1)	End of Week 8 (Cycle 2)
General neurological exam, weight, performance status	X			
Pregnancy test	X 			
Performance status			X 	X 
Neurocognitive testing (Appendix VII)		X 	X 	X 
Adverse event assessment		X	X	X
Patient Questionnaire Booklet 
 
• Brief Fatigue Inventory (BFI)
 
• PROMIS
 
• PRO-CTCAE (for fatigue and cognition items)
 
• Linear Analogue Self-Assessment (LASA)
 
• FACT-Cog
 
• Godin Leisure Time Exercise Questionnaire (GLTEQ)
 
 (Appendices III-VI, XIII, XIV)		X 	X 	X 
Nurse/CRA Phone Contact (Appendix XII)			X	X

1. If the treating physician determines that the woman is of childbearing potential, then a pregnancy test must be done  $\leq$  7 days prior to registration.
2. Patient questionnaire booklets **must** be used; copies are not acceptable for this submission.
3. Must be administered by credentialed personnel. See section 4.1 and appendices VIII and IX.
4. PS will be collected via the Nurse/CRA Phone Contact.
5. Administered at the end of weeks 4 and 8.
6. Baseline assessment must be done  $\leq$  14 days after registration and no more than 7 days prior to 1st day of study drug.
7. +/- 3 days, timing for week 4 and 8 assessments should be measured from time of study drug administration – not baseline.

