## 11.0 TREATMENT EVALUATION

### 11.1 Patient Self-Report Measures

The Patient self-report measures will be given three times, baseline and after weeks 4 and 8 of treatment. These items together take approximately 20 - 25 minutes to complete.

Fatigue is measured by multiple approaches in this protocol to not only provide a complete description of the type of fatigue experienced throughout treatment by the patients but also to inform future studies as to the relative merit (reliability, validity, responsiveness) the alternative methods impart in measuring fatigue.

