## 16.4 Secondary Endpoints

**16.4.1 Other time points:** The same analyses carried out using the 8 week assessment data will be used for analysis of data from the other time point assessments.

**16.4.2 Other fatigue measures:** The other fatigue items ("usual", "usual" and "now") as well as the impact of fatigue items from the BFI, the PRO-CTCAE, and the summated score from the PROMIS fatigue measure will be analyzed separately in turn comparing the average of these variables for each treatment using Kruskal-Wallis testing for change from baseline to four weeks, AUC over the entire treatment period, and repeated measures ANOVA using all treatments and all time points.

**16.4.3 Cognitive function:** The same analyses outlined for the other fatigue measures will be carried out for each of the cognitive function tests.

**16.4.4 Quality of life:** The same analytical approaches will be used to compare the three treatments in terms of QOL as was outlined for the other fatigue measures.

**16.4.5 Safety and tolerability of armodafinil:** Comparison of the proportion of patients reporting adverse events via the CTCAE items will be compared across treatment arms using a Fisher's exact test.

**16.4.6 Area under the curve (AUC) and summary statistics:** For the continuous measures mentioned above, AUC summary statistics will be generated for each patient to represent the overall experience reported by patients for each endpoint (e.g. fatigue) by combining the data from baseline, weeks 4, and 8 assessment points. The average of these AUC variables will be compared between the two treatment arms using two-sample t-tests. Further summary statistics will be constructed for the categorical variables to indicate whether the patient ever responded over the entire treatment period. These categorical variables will be compared between treatment groups via Fisher's exact tests.

**16.4.7 Repeated measures analysis:** The overall experimental layout will be examined via the construction of a repeated measures model using data from all assessment time points involving the continuous variables described above. Tests for time by treatment interaction will be carried out by the profile analysis methods of Srivastava. Covariates such as age, gender and other clinical variables may be included to test their impact on the initial efficacy tests of the primary and secondary analyses described above. Use of the Optune® device will also be included as a descriptive factor.

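### The AUC in 16.4.6 includes the pre-dose score and is tested without baseline adjustment, which costs precision in a secondary analysis

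*Combined protocol and SAP*

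**What the plan says.** Section 16.4.6 defines one AUC per patient for each continuous measure, formed by "combining the data from baseline, weeks 4, and 8 assessment points". It then states: "The average of these AUC variables will be compared between the two treatment arms using two-sample t-tests". It gives no AUC formula and names no covariate.

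The visit times are in Section 11.1: "The Patient self-report measures will be given three times, baseline and after weeks 4 and 8 of treatment". A note to the test schedule in Section 4.0 places the baseline assessment within "14 days after registration and no more than 7 days prior to" the first day of study drug, so it is a pre-dose measurement.

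The AUC reaches most of the secondary programme. Section 16.4.2 analyses the other fatigue measures "using Kruskal-Wallis testing for change from baseline to four weeks, AUC over the entire treatment period, and repeated measures ANOVA". For cognition, Section 16.4.3 says "The same analyses outlined for the other fatigue measures will be carried out for each of the cognitive function tests". For quality of life, Section 16.4.4 says "The same analytical approaches will be used to compare the three treatments in terms of QOL".

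The covariates mentioned elsewhere are the four stratification factors (Section 5.0: chemotherapy, age, corticosteroids, gender) and, optionally, age, gender and other clinical variables (Section 16.4.7). Neither place names the baseline score.

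**The concern.** A score recorded before the first dose cannot carry a treatment effect. Putting it into the outcome and then running an unadjusted test has two consequences. The effect on the AUC is smaller than the effect on the post-dose scores. In addition, stable differences between patients in their starting level stay in the error variance, although the trial has measured them and could remove them.

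At stake is the precision of the summary that 16.4.6 intends as the patient's overall experience, across fatigue, each cognitive test and quality of life. A less precise comparison gives wider intervals and less chance of seeing a real difference in that analysis.

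**Working it through.** **The plan's own figures.** The plan states no power, SD or correlation for any AUC, so there is no AUC figure to reproduce. The only related figure is the arm size in Section 16.2: 100 per arm for 10% versus 25% response, two-sided 5%, 80% power. The uncorrected normal formula reproduces it (n = 100, power 80.2%). The Fisher's exact test that the plan names gives 76.2% by exact enumeration, but that is a separate matter. Only the 100 per arm is used below.

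**Inputs from the documents.** Visits at 0, 4 and 8 weeks (11.1); baseline before dosing (4.0); AUC from all three visits, compared by t-test (16.4.6).

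**Assumptions, because the documents are silent.** Trapezoid rule; equal SDs (set to 1); a common between-visit correlation ρ; a constant effect d at weeks 4 and 8.

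**Step 1: weights.** The trapezoid area divided by 8 weeks is A = Y0/4 + Y4/2 + Y8/4. Baseline has weight 2/8 = 1/4, and the mean difference between arms is (1/2 + 1/4)d = 0.75d.

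**Step 2: unadjusted variance.** The squared weights sum to 1/16 + 1/4 + 1/16 = 0.375. The cross terms sum to 0.625. So V(unadjusted) = 0.375 + 0.625ρ.

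**Step 3: variance after adjusting for Y0.** Cov(A, Y0) = 0.25 + 0.75ρ. So V(adjusted) = 0.375 + 0.625ρ − (0.25 + 0.75ρ)² = 0.3125 + 0.25ρ − 0.5625ρ².

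**Step 4: information lost.** The expected mean difference is 0.75d either way, so the loss is 1 − V(adjusted)/V(unadjusted). The power column shows what the t-test achieves for an effect that the adjusted analysis detects with 80% power (normal approximation, two-sided 5%).

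| ρ | V unadjusted | V adjusted | Loss | 100 per arm is worth | Power of t-test |
|---|---|---|---|---|---|
| 0 | 0.375 | 0.3125 | 17% | 83 | 72% |
| 0.3 | 0.5625 | 0.3369 | 40% | 60 | 58% |
| 0.5 | 0.6875 | 0.2969 | 57% | 43 | 45% |
| 0.7 | 0.8125 | 0.2119 | 74% | 26 | 30% |

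The loss reaches 50% at ρ = 0.42.

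**Step 5: sensitivity to the assumptions.**
- Correlation decaying with time (AR(1)): loss 33% at 0.3, 48% at 0.5, 66% at 0.7.
- Baseline SD a fraction s of the follow-up SD: V(unadjusted) = s²/16 + 0.3125 + ρ(0.375s + 0.25), and V(adjusted) is unchanged. With s = 0.8 and ρ = 0.3 this is 0.04 + 0.3125 + 0.165 = 0.5175, a loss of 35%; at ρ = 0.4 the loss is 44%. With s = 0.6 the loss is 29% at ρ = 0.3 and 48% at ρ = 0.5.

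The reduced-SD rows matter for fatigue. Section 3.1.3 admits only patients scoring at least 6 on the worst-fatigue item, which may narrow the baseline spread and lower the correlation. For s between 0.6 and 0.8 and ρ of 0.3 to 0.4, the loss is roughly 30% to 45%. No score cut-off applies to cognition or quality of life.

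**The case against.** The strongest reply is that this is one secondary summary among several. The primary endpoint is a responder rate built on change from baseline and is not touched. The same measures also get a change-from-baseline analysis, a repeated-measures ANOVA over all visits, and a time-by-treatment test (16.4.7) in which constant level differences between patients cancel. The plan claims no power for any AUC, and the trial's stated aim is preliminary efficacy. All of this stands, and it limits the consequence. It does not remove the point: the change analysis that 16.4.2 states runs only to week 4, and none of these analyses makes the AUC comparison itself more precise.

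A second reply is that the open-ended clinical variables in 16.4.7 could include the baseline score. They are optional and the score is not named; the t-test in 16.4.6 takes no covariate.

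Three stronger readings are tempting, and the documents do not support them.
- A reader might infer that half or more of the information is certainly wasted. That needs ρ of about 0.42 or higher with equal SDs, and the documents give neither quantity.
- A reader might infer that chance baseline imbalance biases the comparison. Under randomisation it does not. The imbalance is the (0.25 + 0.75ρ)² term in Step 3, so it is already counted as imprecision.
- A reader might infer that the AUC is not prorated and that short series are scored as smaller areas, because Section 1.2.1 describes an earlier trial with "The primary end point of prorated Area Under the Curve for the usual fatigue question of the BFI". Here proration is simply not stated. Section 16.8 plans complete-case and several imputation analyses; the first drops a short series and the others fill it. No error can be claimed.

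**Conclusion.** The point holds as a loss of precision. The pre-dose score is part of the AUC, and no baseline adjustment is planned for it. The comparison remains valid, with its type I error intact. The loss relative to a baseline-adjusted AUC is about 40% to 74% for correlations of 0.3 to 0.7, conditional on the trapezoid rule, equal SDs and a common correlation; it may be nearer 30% to 45% for fatigue. Even at zero correlation the loss is 17%, so the direction does not depend on the assumed correlation. The size does, and it cannot be fixed from the documents.

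**What to change.** In 16.4.6, replace the two-sample t-test on the AUC with ANCOVA comparing each armodafinil arm with placebo, using the patient's baseline score on the same measure as covariate. Adding a multiple of a covariate to the outcome changes only that covariate's slope, so the treatment coefficient is the same as for Y4/2 + Y8/4 adjusted for baseline. The baseline component therefore leaves the treatment contrast, and the AUC need not be redefined.

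Two clarifications belong in the same edit. State the AUC formula. Also reconcile the named test: 16.4.2 can be read as placing the AUC under Kruskal-Wallis testing, while 16.4.6 names t-tests between two arms in a three-arm trial.

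The cost is a change of wording in the statistical section. Section 4.0 already schedules a baseline for the questionnaire booklet and the neurocognitive tests, so no new data, visits or patients are needed.

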## 16.5 Statistical Design

The primary endpoint for the trial is the response rate in terms of a clinically meaningful improvement in patient-reported fatigue, defined as at least a two-point improvement in fatigue as measured by the usual fatigue item from the Brief Fatigue Inventory at 8 weeks. This change

will be from baseline to 8 weeks (after randomization). The design proposed for this study will randomize a maximum of 330 evaluable patients to one of three treatment arms.

**Efficacy stopping rules:** This study will be monitored by Alliance Data and Safety Monitoring Board (DSMB) every 6 months for safety and efficacy. If at any time prior to full accrual the p-value for the Fisher's exact test that an arm is superior to the other arm given all available data falls below 0.001 then consideration will be given to stopping the trial early.

## **16.6 Adverse Event Stopping Rule**

The stopping rule specified below is based on the knowledge available at study development. We note that the Adverse Event Stopping Rule may be adjusted in the event of either 1. the study re-opening to accrual or 2. at any time during the conduct of the trial and in consideration of newly acquired information regarding the adverse event profile of the treatment(s) under investigation. The study team may choose to suspend accrual because of unexpected adverse event profiles that have not crossed the specified rule below.

Accrual will be temporarily suspended to this study if at any time we observe grade 4 or higher events considered at least possibly related to study treatment (i.e. an adverse event with attribute specified as "possible", "probable", or "definite") that satisfy the following:

- If 3 or more patients in the first 20 treated patients (or 10% of all patients after 20 are accrued) experience a Grade 4 or higher non-hematologic adverse event and the adverse event rate is higher on either armodafinil arm than the placebo.

We note that we will review Grade 4 and 5 adverse events deemed "unrelated" or "unlikely to be related", to verify their attribution and to monitor the emergence of a previously unrecognized treatment-related adverse event.

## **16.7 Study Monitoring**

This study will be monitored by the Clinical Data Update System (CDUS) version 3.0. Cumulative CDUS data will be submitted quarterly to CTEP by electronic means. Reports are due January 31, April 30, July 31, and October 31. Instructions for submitting data using the CDUS can be found on the CTEP web site [REDACTED]

The principal investigator(s) and the study statistician will review the study at least twice a year to identify accrual, adverse event, and any endpoint problems that might be developing. This study will be monitored by the Alliance Data and Safety Monitoring Board (DSMB), an NCI-approved functioning body. Reports containing efficacy, adverse event, and administrative information will be provided to the DSMB every six months as per NCI guidelines.

**16.7.1** We will further carry out a single interim analysis when 30 patients per treatment arm are evaluable for the primary endpoint. We will use this interim analysis to verify that the 250 mg. dose arm is worthy of further accrual. If the conditional probability is less than 1% that the effect size is at least of moderate size given, the results (effect size) at that point, the 250 mg. dose arm will be considered for closing.

## **16.8 Missing Data**

Routines developed by Mayo Clinic Cancer Center statisticians will be used to handle missing data in a number of ways including complete case analysis and imputation via nearest neighbor, mean value, last value, and zero value carried forward approaches. Multiple approaches are used so that the sensitivity of results to alteration in imputational assumptions may be assessed. The extent of missing data on the primary and secondary endpoints will be explored for non-random influences. Sensitivity analysis will be performed using various imputation techniques, to ensure

results are not unduly influenced by the presence of missing data. Other endpoints will be handled in a similar fashion (99).

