#### 11.1.1 Brief Fatigue Inventory (BFI)

The BFI is a 9-item instrument that allows for the rapid assessment of fatigue level in cancer patients and identifies those patients with severe fatigue. Three items ask patients to rate their fatigue for “now,” and fatigue at its “worst” and “usual” for the last 24 hours. The 11-point scales are bounded by 0 = “no fatigue” and 10 = “fatigue as bad as you can imagine.” Using the same type of scales, the remaining questions ask patients to rate how their fatigue interferes with several quality of life domains including general activity, walking, mood, work, and relations with others. These scales are bounded by 0 = “does not interfere” and 10 = “interferes completely.” The reliability and validity of the BFI were demonstrated in a study of 305 cancer patients and 290 community-dwelling adults. An internal consistency coefficient (Cronbach’s alpha) = 0.96 was demonstrated when the BFI was administered to 305 patients with cancer (80). The BFI has been demonstrated as viable primary endpoints for numerous cancer clinical trials and has been translated into 22 different languages (81).

Single-question assessment is the most commonly used and the most useful methodology. A score of 1–3 indicates the presence of mild fatigue that does not require clinical intervention, and scores of 4–6 and 7–10 indicate moderate and severe fatigue, respectively, which require further evaluation and clinical intervention (82).

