### **11.1.5 FACT-Cog (Secondary Cognitive Endpoint)**

Patients in this study will self-report their perceived cognitive functioning using the FACT-Cog version 3 (92). For many cancer-related symptoms, given their subjective nature, self-report is the only way an assessment can be conducted. The FACT-Cog is a useful measure of perceived cognitive deficits and related quality of life for adults undergoing chemotherapy, and is the first patient-reported outcomes measure to be developed and validated with a sample of cancer patients. The scale measures the frequency of positive and negative cognitive functioning events over the past seven days, based on self-report. The measure utilizes a five-point Likert-type scale (ranging from 0 = never to 4 = several times a day) to assess several different aspects of cognitive function. Lower scores are indicative of poorer perception of functioning. The FACT-Cog assesses a broad range of cognitive domains (not just those specifically related to work) and provides a multidimensional view of the cognitive deficits often experienced by patients with cancer.

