## 13.0 TREATMENT/FOLLOW-UP DECISION AT EVALUATION OF PATIENT

If the patient discontinues the study agent prior to 8 weeks, the patient will go off study.

A patient is deemed *ineligible* if after registration, it is determined that at the time of registration, the patient did not satisfy each and every eligibility criteria for study entry. If the patient received treatment, all data up until the point of confirmation of ineligibility must be submitted. If the patient never received treatment, on-study material must be submitted.

A patient is deemed a *major violation*, if protocol requirements regarding treatment in cycle 1 of the initial therapy are severely violated that evaluability for primary end point is questionable. All data up until the point of confirmation of a major violation must be submitted.

A patient is deemed a *cancel* if he/she is removed from the study for any reason before any study treatment is given. On-study material and the End of Active Treatment/Cancel Notification Form must be submitted. No further data submission is necessary.

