### 16.3 Primary Endpoint

The primary endpoint of this trial is the response rate in terms of a clinically meaningful improvement in patient-reported fatigue at 8 weeks. A response is defined as an improvement of 2 points on the 0-10 scale of the usual fatigue on the BFI.

All patients meeting the eligibility criteria who have signed a consent form, have begun treatment, and have not had a major treatment violation within the 1st cycle of treatment will be evaluable for the primary endpoint. Patients will be analyzed according to the arm in which they were randomized.

Comparison of the primary endpoint between arms will be based on a binomial point estimate computed for each arm and a Fisher's exact test will be the inferential hypothesis test.

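### Read literally, the zero-value imputation in Section 16.8 scores BFI dropouts as responders, so that one sensitivity analysis favours whichever arm loses more patients

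*Combined protocol and SAP*

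**What the plan says.** Section 16.8 (Missing Data) relies on in-house routines. It lists complete-case analysis together with "imputation via nearest neighbor, mean value, last value, and zero value carried forward approaches", covers the primary and secondary endpoints, and treats other endpoints similarly. The stated purpose is comparative: "Multiple approaches are used so that the sensitivity of results to alteration in imputational assumptions may be assessed". No method is named as primary, and zero is not defined for any scale.

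Four other parts of the plan determine what a zero does:

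- **Scale direction.** Section 11.1.1 describes the BFI fatigue items as "bounded by 0 = “no fatigue” and 10 = “fatigue as bad as you can imagine", so 0 is the best score.
- **Response.** Section 16.5 gives the primary endpoint as a response rate, "defined as at least a two-point improvement in fatigue as measured by the usual fatigue item from the Brief Fatigue Inventory at 8 weeks". Section 16.3 agrees: "A response is defined as an improvement of 2 points on the 0-10 scale of the usual fatigue on the BFI".
- **Early stopping.** Section 13.0: "If the patient discontinues the study agent prior to 8 weeks, the patient will go off study". A week-8 BFI is then expected to be missing.
- **Evaluability.** Section 16.3 asks for eligibility, consent, treatment started and no major treatment violation in cycle 1. It does not ask for a week-8 score.

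For FACT-Cog, Section 11.1.5 runs the scale the other way: "Lower scores are indicative of poorer perception of functioning".

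**The concern.** Entering zero for a missing value is conservative only where low scores are bad. On the BFI it is the most favourable value available. A patient who stops for toxicity, goes off study and has no week-8 score stays in the denominator and, under a literal zero, is recorded as free of fatigue. If baseline usual fatigue was 2 or more, that patient is a responder.

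The response rate in this analysis then rises with the dropout rate. An analysis meant to show whether missing data drive the result would itself be driven by them. It could appear to confirm a benefit in an arm that patients leave more often, or cast doubt on a correct result when placebo loses more. Even when dropout is equal, both arms move towards the same high rate and a real difference is diluted.

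**Working it through.** **Inputs from the documents.** Section 16.2: 100 evaluable patients per arm, 10% response on placebo, 25% on armodafinil, two-sided 5% for each comparison with placebo. Section 16.3: Fisher's exact test.

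**Assumed inputs.** The missing fraction m in each arm, and q, the share of dropouts with baseline usual fatigue of at least 2. Entry (Section 3.1.3) requires 6 or more on the worst-fatigue item and sets no threshold for usual fatigue. So q should be close to 1 but is not guaranteed; 1.0 and 0.90 are used.

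**Step 1: the plan's own figure.** With the pooled-variance formula and a mean rate of 0.175,

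n = [1.960 × √(2 × 0.175 × 0.825) + 0.842 × √(0.10 × 0.90 + 0.25 × 0.75)]² / 0.15² ≈ 99.5, or 100 per arm, with 80.2% power.

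This reproduces the plan. Exact enumeration of Fisher's test at 100 per arm gives 76.2%, which is the reference for power below.

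**Step 2: response rate after imputation.** With response p among observed patients:

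- zero entered as a score: m × q + (1 − m) × p
- missing counted as non-response: (1 − m) × p

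For example, with m = 0.20, q = 1 and p = 0.10, zero gives 0.20 + 0.80 × 0.10 = 28.0%, and non-response gives 0.80 × 0.10 = 8.0%.

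**Step 3: no drug effect (p = 10% in both arms, q = 1).** The chances are for a significant result favouring the first-named arm, by exact enumeration at 100 per arm.

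| Missing, arm A vs arm B | Rates with zero | Chance favouring A | Rates with non-response | Chance favouring A |
|---|---|---|---|---|
| 0% vs 0% | 10.0% vs 10.0% | 1.4% | 10.0% vs 10.0% | 1.4% |
| 10% vs 10% | 19.0% vs 19.0% | 1.6% | 9.0% vs 9.0% | 1.4% |
| 15% vs 10% | 23.5% vs 19.0% | 8.7% | 8.5% vs 9.0% | 1.0% |
| 20% vs 10% | 28.0% vs 19.0% | 26.6% | 8.0% vs 9.0% | 0.7% |
| 25% vs 10% | 32.5% vs 19.0% | 52.9% | 7.5% vs 9.0% | 0.5% |

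Arm A can be either arm: 20% missing on placebo against 10% on armodafinil gives 26.6% in favour of placebo. With q = 0.90, 20% vs 10% missing becomes 0.20 × 0.90 + 0.80 × 0.10 = 26.0% against 18.0%, and the chance is still 22.2%.

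**Step 4: a true effect of 10% vs 25%.** With 10% missing in each arm, zero gives 0.10 + 0.90 × 0.10 = 19.0% against 0.10 + 0.90 × 0.25 = 32.5%. The 15-point difference shrinks to 13.5 points on a higher base, and power falls from 76.2% to 52.9%. Non-response imputation gives 9.0% against 22.5% and power of 70.4%. With 20% missing on placebo and 10% on armodafinil, zero gives 28.0% against 32.5% and power of 7.8%.

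**Step 5: one data set.** Take 9 responders of 90 observed with 10 missing, against 7 of 70 observed with 30 missing, so 10% among observed patients in both arms. Complete-case p = 1.0. Zero gives 19/100 vs 37/100, p = 0.007. Non-response gives 9/100 vs 7/100, p = 0.80.

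**Step 6: other scales.** Zero is the worst value on FACT-Cog as Section 11.1.5 scores it, and no words on Controlled Oral Word Association is also worst. It cannot occur on the PROMIS fatigue form, where seven items scored 1 to 5 have a minimum sum of 7. As a Trail Making time it is best or impossible. If PRO-CTCAE answers are scored from 0, it is the best answer.

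**The case against.** **Zero may not mean a score of 0.** The in-house routines and the cited reference cannot be seen. They might impute zero change, or reverse the scale first, and either would make the dropout a non-responder. This stands as a limit: the result is conditional on the literal reading. But zero is listed beside mean and last values, which are scores, and the text states neither alternative.

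**It is one branch of several.** This also stands. The complete-case and last-value analyses do not share the flaw. If last value can carry the baseline score, a patient who leaves before week 4 has no change and is already a non-responder there. A reader might infer from the table that the trial's false-positive rate is 27% or 53%. The documents do not support that, because Section 16.3 does not mention the zero branch and no decision is tied to it. The figures are the chance that this one sensitivity result is significant.

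**The direction is not known.** A reader might infer that the method favours armodafinil. Section 8.0 stops treatment for serious related toxicity, and Section 15.1.7 describes several side effects as dose related, so greater loss on armodafinil is plausible. The documents forecast no dropout, however, and the bias follows the missing data either way.

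**Zero is not wrong everywhere.** It is tempting to call it impossible on the LASA. Appendix V asks for a number from 0 to 10 while its printed rows run from 1 to 10, so this is not shown. On LASA items 1 to 6 a zero would be the unfavourable end; on the pain and fatigue items it would be the favourable end or off the printed row.

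**Some dropouts may be excluded.** If an early stop were classed as a major cycle 1 violation, that patient would not be evaluable and m would be smaller. Stopping for toxicity under Section 8.0 follows the protocol, so it should not by itself count as one.

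**Conclusion.** The point holds for the zero-value branch as written. Under the literal reading, an evaluable dropout with baseline usual fatigue of at least 2 becomes a responder, and this sensitivity analysis leans towards the arm with more missing week-8 scores. A five-point gap in missing data has a modest effect; gaps of ten to fifteen points have a large one. Equal missingness leaves the null comparison essentially unbiased but costs considerable power.

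The sizes rest on assumed missing fractions, the same 10% response among observed patients in both arms under the null, nearly all dropouts having baseline usual fatigue of 2 or more, and 100 evaluable patients per arm. The documents do not show that the primary result is biased, that all the missing-data analyses are biased, or that armodafinil is systematically favoured. The correction is worth making because the rule works against its own stated purpose on the primary endpoint and is cheap to repair.

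**What to change.** In Section 16.8:

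1. For the BFI responder endpoint, replace zero-value imputation with non-responder imputation: a missing week-8 usual-fatigue score counts as no response.
2. For other scores, do not enter a raw 0 where 0 is the best value or lies outside the scale. This covers the BFI items, PRO-CTCAE, PROMIS fatigue, Trail Making time, and the LASA pain and fatigue items. Use either zero change from baseline or an unfavourable value in that scale's own direction, and state the choice for each endpoint. Zero can stay where it is a valid unfavourable score.
3. If zero change was intended all along, say so; for the BFI responder endpoint that is equivalent to item 1.

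The cost is a few sentences and a small change to the imputation routine, with no effect on enrolment or patient procedures. The downside is that this sensitivity analysis will show lower response rates. Non-response imputation also loses some power (70.4% against 76.2% at 10% missing in each arm) and is unfavourable to the arm with more dropout, so it should be read beside the complete-case and last-value results.
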